1. PROCEDURE

The research consists on studying the effects of tDCS in combination with cognitive behavioural therapy (CBT) in adults diagnosed with gambling disorder that attend the UK National Problem Gambling Clinic. The design of the study consists on a double blind randomized control interventional trial with parallel assignment (two interventions – tDCS in combination with CBT that will be evaluated against CBT alone).

Participants will be split in two groups depending on the treatment they receive. The treatment groups will be: tDCS real stimulation with CBT or tDCS sham with CBT. Real stimulation condition involves the application of tDCS stimulation for 20 minutes whereas sham condition is used as a control (similar to a placebo).

The investigators aim to have a total of 32 participants diagnosed with gambling disorder based on the Problem Gambling Severity Index (PGSI). There will be 16 participants per condition, having two conditions (real stimulation and sham).

Treatment 1. Participants will attend 8 weekly sessions where they receive tDCS real stimulation while complete CANTAB cognitive tasks to measure cognitive functions and following this, they will attend a CBT session.

Treatment 2. Participants will attend 8 weekly sessions where they receive sham tDCS, while complete CANTAB cognitive tasks to measure cognitive functions and following this, they will attend a CBT session.

Primary endpoint/outcomes

1. Change in scores on the Yale-Brown Obsessive Compulsive Scale adapted for Pathological Gambling (PG-YBOCS). [Time Frame: Change from baseline PG-YBOCS scores at week 2, 3, 4, 5, 6, 7 and 8].
2. Change in scores on the Visual Analogue Scale (VAS). [Time Frame: Change from baseline VAS scores at week 2, 3, 4, 5, 6, 7 and 8].
3. Change in scores on the Gambling Symptom Assessment Scale (G-SAS). [Time Frame: Change from baseline G-SAS scores at week 8].
4. Change in scores on the Cambridge Gambling Task (CGT). [Time Frame: Change from baseline CGT scores at week 8].

Secondary endpoints/outcomes

1. Change in scores on the Information Sampling Task (IST). [Time Frame: Change from baseline IST scores at week 2, 3, 4, 5, 6, 7 and 8].

2. Change in scores on the Stop Signal Task (SST). [Time Frame: Change from baseline IST scores at week 2, 3, 4, 5, 6, 7 and 8].
3. Changes in encephalography (EEG) neural oscillatory activity. [Time Frame: Correlation of tDCS and EEG activity in weeks 1, 2, 3, 4, 5, 6, 7 and 8].

Primary objective

The main objective is to study whether 8 weekly sessions during 8 consecutive weeks of tDCS simulation will help to decrease cravings and addiction symptoms such as risk-taking behaviour and impulsivity in patients diagnosed with gambling disorder attending the UK National Problem Gambling Clinic, exploring whether tDCS combined with CBT will improve the treatment outcomes – reducing significantly more the symptomatology, compared to CBT treatment alone.

Hypothesis 1:

Null hypothesis (H_0): The primary outcome measures results will be the same in the group of participants that receive tDCS real stimulation combined with CBT and the control group (sham tDCS + CBT).

Alternative hypothesis (H_A): The primary outcome measures results will not be the same in the group of participants that receive tDCS real stimulation combined with CBT and the control group (sham stimulation + CBT).

Hypothesis 2:

H_0 : The primary outcome measures results obtained in the baseline will be the same to the outcome measures results at the end of the treatment.

H_A : The primary outcome measures results obtained in the baseline will not be the same to the outcome measures results at the end of the treatment.

Secondary objectives

To investigate if electrophysiological measures (EEG resting state) predict behavioural outcomes obtained from the cognitive task performance during tDCS experiments, as well as studying the task performance progression comparing every week's results to the baseline.

Hypothesis 1:

H_0 : The secondary outcome measures results obtained from the EEG resting state will be the same in the group of participants that receive tDCS real stimulation combined with CBT and the control group (sham tDCS + CBT).

H_A : The secondary outcome measures results obtained from the EEG resting state will not be the same in the group of participants that receive tDCS real stimulation combined with CBT and the control group (sham tDCS + CBT).

Hypothesis 2:

H_0 : The secondary outcome measures results obtained in the baseline will be the same to the outcome measures results at the end of the treatment.

H_A : The secondary outcome measures results obtained in the baseline will not be the same to the outcome measures results at the end of the treatment.

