2. MATERIALS

Participants

The sample size will be 16 participants per group (2 groups) that attend 8 treatment sessions.

Inclusion criteria

Male or females between 18 and 65 years of age diagnosed with disordered gambling based on the Problem Gambling Severity Index (PGSI) who can speak and read English, capable of giving informed consent, and don't have any of the exclusion criteria.

Minimum Age: 18 Years

Sex: All

Gender Based: No

Accepts Healthy Volunteers: No

Exclusion criteria

- a. History or evidence of chronic or residual neurological disease.
- b. A pacemaker or deep brain stimulation.
- c. Metal implants in head or neck area (e.g. postoperative clips after intracerebral aneurysm; arterial aneurysm in the vascular system, implantation of an artificial hearing aid).
- d. Intracerebral ischemia/history of bleeding.
- e. Prior evidence of epileptic seizures, history of epilepsy.
- f. History of head injury with loss of consciousness.
- g. Any serious medical conditions (disease of the internal organs).
- h. Pregnancy or breast-feeding.
- i. Negative screening from the clinic psychiatrist

Software

This research uses a CE marked medical device, transcranial direct current stimulation (tDCS) built in the international company Neuroelectrics (<https://www.neuroelectrics.com/products/>). Specifically, Starstim® is a wireless hybrid EEG/tCS neurostimulator system. It includes the comfortable neoprene head cap where the electrodes can be easily inserted. Starstim® complies with the European legislation for clinical research.

Cognitive and physiological measurement tools

Primary outcomes:

1. Yale-Brown Obsessive Compulsive Scale adapted for Pathological Gambling (PG-YBOCS): it is a 10-item questionnaire that measures the gambling severity. The scores range from 0 to 4. The questions 1 to 5 assess urges and thoughts associated with gambling disorder, and the rest of the questions assess the behavioural component of the disorder in the past week. The total score will be calculated as well as the separate scores. Gambling severity will be higher with higher scores (we will obtain measures of PG-YBOCS in all sessions 1,2,3,4,5,6,7 and 8).

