2. Visual Analogue Scale (VAS) for gambling cravings: it is a horizontal line which length is 100 mm where the left side corresponds to the lower score and the right side to the highest score (it ranges from 0 to 10). The participant will draw a line starting from the lowest level to the level that better represents their gambling cravings at the current time. The score will be calculated by measuring this line (in millimetres). The gambling cravings will be higher with higher VAS scores (we will obtain measures of VAS in all sessions 1,2,3,4,5,6,7 and 8).
3. Gambling Symptom Assessment Scale (G-SAS): it is a 12-item scale to measure gambling symptoms. Each of the 12 questions has a score ranging from 0 to 4 based on the last week, which makes it useful to measure changes during treatment. The total score ranges from 0 to 48. The symptoms severity will be higher with higher G-SAS scores.
4. Cambridge Gambling Task (CGT): it is a cognitive task that dissociates risk taking from impulsivity, because in the ascending bet condition the participant who wants to make a risky bet has to wait patiently for it to appear (10 minutes). <http://www.cambridgecognition.com/cantab/cognitive-tests/executive-function/cambridge-gambling-task-cgt/>

Secondary outcomes:

1. Information Sampling Task (IST): it tests impulsivity and decision making. The participant is instructed that they are playing a game for points, which they can win by making a correct decision (up to 15 minutes). <http://www.cambridgecognition.com/cantab/cognitive-tests/information-sampling-task-ist/>
2. The Stop Signal Task (SST): it measures response inhibition or impulse control (up to 20 minutes). <http://www.cambridgecognition.com/cantab/cognitive-tests/executive-function/stop-signal-task-sst/>
3. Encephalography (EEG) activity: EEG resting state oscillatory neural activity will be obtained before and after tDCS stimulation to study the correlation of tDCS effects and neurophysiological changes in the brain.

Trial design

- Study Type: Interventional
- Primary Purpose: Treatment
- Framework: Superiority (Treatment will be superior to placebo (sham condition)).
- Interventional Study Model: Parallel Assignment. Investigation of the effects of transcranial direct current stimulation (tDCS) in combination with cognitive behavioural therapy (CBT) against the effects of CBT alone.
- Number of Arms: 2

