5. STATISTICAL ANALYSIS PLAN

Data source

Behavioural data sets will be obtained from computer-based cognitive tasks and questionnaires that participants complete during the stimulation sessions. The results obtained from completing these tasks and questionnaires generate measures for addiction-related symptoms such as cravings, impulsivity, risk-taking behaviour, delay aversion and control inhibition. Each participant will produce data at two time points for G-SAS and CGT measures and at eight time points for VAS, PG-BOCS and secondary measures. Electroencephalography (EEG) resting state neural oscillatory activity will be recorded for 5 minutes prior and 5 minutes after the tDCS intervention.

Analysis objectives

The investigators will study whether the behavioural and cognitive data obtained from participants in different time points are significantly different between the two treatment groups. In addition, the investigators will investigate if electrophysiological measures (EEG resting state) predict behavioural outcomes obtained from the cognitive task performance during tDCS experiments, as well as studying the task performance progression comparing every week's results to the baseline.

Analysis sets/Subgroups

The following data sets subgroups will be analysed:

1. Experimental - Stimulation with CBT: Participants that attend to 8 weekly sessions of tDCS stimulation and that following the tDCS session, they attend to a cognitive behavioural therapy (CBT) session.
2. Sham Comparator - Sham with CBT: Participants that attend to 8 weekly sessions of sham tDCS and that following the tDCS session, they attend to a CBT session.

The aim is to study whether the combination of stimulation and therapy help to improve the treatment outcomes in comparison with CBT alone.

Variables and covariates

Primary Dependent Variables:

1. Pathological Gambling adapted Yale-Brown Obsessive Compulsive Scale (PG-YBOCS) scores for gambling severity.
2. Visual Analog Scale (VAS) scores for gambling cravings.
3. Gambling Severity Symptoms Assessment (G-SAS) for gambling symptoms.
4. Cambridge Gambling Task's (CGT) scores for gambling behaviour.

Secondary Dependent Variables:

1. Stop signal task's (SST) scores for inhibition control.
2. Information Sampling Task's (IST) scores for impulsivity.
3. EEG resting state oscillatory neural activity.

Independent Variables:

1. tDCS condition (Stimulation or Sham)
2. Time (sessions 1 to 8)

Covariates:

1. Age
2. Gender

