Handling of missing values

We expect to have very few cases of missing values due to the methodology used in the study. The variables will be measured with a computer software that doesn't allow to continue with the test unless one of the options is selected. The only possible missing values would come by an error on the whole task, which will result in no data at all. In this case, we would withdraw this participant from the analysis of that specific task.

The possible missing values that we would expect to deal with, will come from the covariates measures that are obtained from paper-based questionnaires. The researcher checks before the participant leaves the session that they have completed all the questions. However, if we have to deal with missing values, we will use common-point imputation that is commonly used for rating scales, which is the case in our questionnaires. With this technique we would use the most commonly chosen value for the rest of the questions and substitute it for the missing value

Statistical Procedures

The analysis performed will be as in Loo et al (2012): the two treatment groups will be analysed for differences in demographic and clinical variables at baseline using χ^2 -tests for categorical variables

and t-tests for continuous variables. To test the effect of tDCS on test performance, a 2 x 2 mixed between-within ANOVA will be conducted. The between-groups factor will be stimulation condition (real stimulation vs sham) and the within-participants factor will be time (change from baseline). Analyses will test for main effects of stimulation condition and session as well as the stimulation-session interaction.

Secondary measures involve cognitive tasks and EEG resting state neural oscillations recording. Differences between sessions scores will be analysed with mixed between-within repeated measures ANOVA. The between-groups factor will be tDCS condition (real tDCS vs sham tDCS) and the within-participants factor will be time (change from baseline). Analysis will test for main effects of group (tDCS condition) as well as for tDCS-time interaction to investigate the presumable accumulative effects of tDCS. This analysis will serve to study if specific EEG resting state oscillatory activity correlates with the modulatory effect of tDCS on task performance and to explore the presumable accumulative effect of tDCS across time.

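### Four unranked primary outcomes share one null hypothesis with no stated alpha, deciding effect or multiplicity rule; at an assumed 5% and one contrast each, a false arm difference is about 9–19% likely (between-outcome correlation 0.9 to 0)

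*Combined protocol and SAP*

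**What the plan says.** Section 1 (Primary endpoint/outcomes) lists four primary outcomes: PG-YBOCS, VAS, G-SAS and CGT, each as a change from baseline. For PG-YBOCS and VAS the time frame covers seven post-baseline weeks (for VAS, "Change from baseline VAS scores at week 2, 3, 4, 5, 6, 7 and 8"); for G-SAS and CGT it is week 8 only. Section 5 (Variables and covariates) repeats the same four as primary dependent variables. They are numbered, but no order of importance is given.

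Under Primary objective, Hypothesis 1 has one null and one alternative for all four: "The primary outcome measures results will not be the same in the group of participants that receive tDCS real stimulation combined with CBT" and the sham group. The objective aims at "reducing significantly more the symptomatology, compared to CBT treatment alone", and Trial design in section 2 gives "Framework: Superiority (Treatment will be superior to placebo (sham condition". For PG-YBOCS, section 2 adds: "The total score will be calculated as well as the separate scores".

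Section 5 (Statistical Procedures) begins "The analysis performed will be as in" a cited 2012 study. It then says "a 2 x 2 mixed between-within ANOVA will be conducted", with tests of the stimulation main effect, the session main effect and their interaction. The within-person factor is time, glossed as change from baseline, whereas Variables and covariates defines it as "Time (sessions 1 to 8". Age and gender are listed as covariates. Nowhere does the document state a significance level, a multiplicity adjustment, a hierarchy or the effect that decides Hypothesis 1.

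**The concern.** Hypothesis 1 is the efficacy question of a trial framed as superiority. Its null says that the primary results are the same in both arms, so a difference on one outcome is enough to contradict it. Without a rule fixed in advance, one nominally significant result among four could be reported as rejecting the null when tDCS adds nothing to CBT. The error rate of that conclusion is the family-wise rate over the four outcomes, not the rate of a single test. With 32 participants, a positive result will be credible only if the rule was written before the data were seen.

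**Working it through.** **Inputs from the document.** Four primary outcomes; 16 per arm (32 in total); a non-directional alternative; a superiority claim. The sample size comes with no alpha, power, effect size or SD, so it cannot be reproduced. It is not needed for the error rate beyond fixing 30 degrees of freedom.

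**Assumptions, because the document gives no figure.** Two-sided 5% per outcome (2.5% in the favourable direction); one between-arm contrast per outcome; a difference on any one outcome counts; no true effect; common between-outcome correlation r from 0 to 0.9.

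**Step 1: independent outcomes.** The family-wise error is 1 − (1 − α)^k.
- Any of four, either direction: 1 − 0.95^4 = 18.5%.
- Any of three, favouring tDCS: 1 − 0.975^3 = 7.3%.

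**Step 2: correlated outcomes, by simulation.** The four-outcome column uses equicorrelated normal statistics (400,000 runs). Simulated 16 v 16 t-tests agree within about half a percentage point. The three-scale column uses simulated 16 v 16 t-tests (100,000 runs).

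| r | Any of four, either direction | Any of PG-YBOCS, VAS, G-SAS, favouring tDCS |
|---|---|---|
| 0 | 18.5% | 7.3% |
| 0.3 | 17.3% | 6.6% |
| 0.5 | 15.6% | 6.3% |
| 0.7 | 13.0% | 5.5% |
| 0.9 | 9.5% | 4.3% |

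The excess vanishes only at perfect correlation, where the rates return to 5% and 2.5%. The lower end of the range is a cut-off at r = 0.9, not a bound (about 8% at 0.95).

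**Step 3: a more structured case.** Three overlapping self-report scales are unlikely to be uncorrelated. If they correlate 0.3, 0.5, 0.7 or 0.9 with each other and CGT is uncorrelated with them, the chance of any false difference is 17.9%, 17.0%, 15.5% or 13.1%.

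**Step 4: cost of a correction.** Holm compares the ordered p-values with 0.05/4 = 1.25%, 0.05/3 = 1.67%, 0.05/2 = 2.5% and 5%. Power for a two-sample t-test comes from the noncentral t with 30 df and noncentrality d × √(16/2) = 2.83d.
- At 5%, 80% power needs d = 1.02; at 1.25% it needs d = 1.25.
- At d = 1.02, power at 1.25% is about 59%. That is the case where only one outcome responds.
- If all four respond at 1.02 SD, Holm's later steps raise power to about 67–71% per outcome, depending on r.

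**The case against.** - **The trial is exploratory.** It is a small, single-centre educational project, and the objective uses the word exploring. That makes the choice between Holm and a single primary outcome the sponsor's to make. It does not remove the need for a rule: the same sentence seeks a significantly larger reduction, the framework is superiority, the hypotheses are formal, and nothing labels the results exploratory.
- **The alpha may be in the cited study.** That is possible, and the study cannot be seen here. A reader should not infer that no alpha exists anywhere, only that this plan states none. A borrowed alpha would still not say how these four outcomes combine under this null.
- **Requiring all four outcomes would control the error.** It would, at no more than 5%, but no such rule is written and the literal null points the other way.
- **A reader might infer a 5–10% chance of a false result favouring tDCS across all four outcomes.** The document does not support this. It says that higher scores are worse for PG-YBOCS, VAS and G-SAS but gives no scoring direction for CGT, so only the 4–7% for the three scales can be derived.
- **A reader might infer 18–34%, by counting both the main effect and the interaction.** The plan lists both tests but does not say that either one is enough, so this is not an estimate for the plan as written.
- **A reader might infer that the main effect must be the wrong test because it averages in baseline.** That is one reading. If change scores are analysed, the main effect is itself an arm difference in change. The text leaves this open, which is why the deciding effect needs naming.
- **Hypothesis 2 is also untreated.** It is a separate within-participant null and need not be relabelled to control Hypothesis 1.

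**Conclusion.** The point stands. The plan has four unranked primary outcomes, a single null that any one of them can contradict, and no stated alpha, deciding effect or multiplicity rule. Under the assumptions listed above, the chance of at least one false arm difference is about 9–19% (13–18% in the structured case), roughly two to four times the 5% of a single test. The chance of a false result favouring tDCS on the three directional scales is about 4–7%, against 2.5%. The per-test 5%, the correlations and the single contrast per outcome are assumptions. The absence of a rule is not; it can be read directly from the text. This should be fixed before analysis, and text changes are enough.

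**What to change.** Amend the endpoint list and Hypothesis 1 in section 1, and Statistical Procedures in section 5:

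1. State a two-sided 5% level.
2. Name one deciding between-arm contrast in change from baseline for each primary outcome. For PG-YBOCS and VAS, choose in advance either week 8 or the average over weeks 2–8. Specify the PG-YBOCS total, one CGT measure with its favourable direction, and whether age and gender are adjusted for.
3. Apply Holm across the four, which holds the family-wise rate at or below 5% whatever the correlation. Claim superiority only for outcomes that survive in favour of tDCS.
4. Label other effects, weeks and subscores that bear on Hypothesis 1 as supportive.
5. Reconcile the two-level time factor implied by "a 2 x 2 mixed between-within ANOVA will be conducted" with "Time (sessions 1 to 8".

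The alternative is to name a single primary outcome, which has no alpha cost.

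**Cost.** No new data. Holm costs the power shown in step 4 of the working: at 1.02 SD it falls from 80% to about 59% if only one outcome responds. A week-8 contrast would make weeks 2–7 supportive for PG-YBOCS and VAS, although they are now in the primary time frame. A single PG-YBOCS primary would make VAS, G-SAS and the CGT measures of risk-taking and impulsivity supportive.

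### Primary Hypothesis 2 is a before-after null that names no arm; rejecting it cannot support a tDCS claim, yet it ranks equally with Hypothesis 1 and the SAP does not say which ANOVA term decides

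*Combined protocol and SAP*

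**What the plan says.** Section 1 (Procedure, Primary objective) asks whether tDCS added to CBT improves outcome, in the words "reducing significantly more the symptomatology, compared to CBT treatment alone". Two hypotheses follow, each with a formal null and alternative. Hypothesis 1 is between arms; its null begins "The primary outcome measures results will be the same in the group of participants that receive tDCS real stimulation combined with CBT" and goes on to name the sham control. Hypothesis 2 has the null "The primary outcome measures results obtained in the baseline will be the same to the outcome measures results at the end of the treatment" and the alternative "The primary outcome measures results obtained in the baseline will not be the same to the outcome measures results at the end of the treatment". It mentions neither arm. The secondary objectives contain a Hypothesis 2 of the same form.

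The SAP (section 5, Analysis sets/Subgroups) gives CBT to both groups. The experimental set is "Participants that attend to 8 weekly sessions of tDCS stimulation and that following the tDCS session", and the entry goes on to add CBT. The comparator set is "Participants that attend to 8 weekly sessions of sham tDCS and that following the tDCS session, they attend to a CBT session". Section 2 (Trial design) sets a superiority framework of real stimulation over sham.

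For the analysis, section 5 (Statistical Procedures) specifies a 2 x 2 mixed ANOVA and says: "Analyses will test for main effects of stimulation condition and session as well as the stimulation-session interaction". It does not say which of the three terms answers the primary question. No significance level is given, and Hypotheses 1 and 2 are not ranked.

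**The concern.** The trial randomises tDCS, not CBT. A before-after comparison that ignores arm picks up everything that moves scores during treatment. All participants receive CBT. They are recruited when they contact the clinic for help (section 2, Trial setting), so regression to the mean is plausible. One primary outcome, the Cambridge Gambling Task, is a performance test taken twice, so practice may add to change on that measure. None of these sources depends on stimulation.

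What is at stake is interpretation. As written, a primary null can be rejected when the two arms behave identically, and nothing in the plan says that such a result leaves the tDCS question unanswered.

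**Working it through.** **Which term tests which hypothesis.** Let the mean change from baseline be μ in the sham arm and μ + δ in the real arm, where δ is the tDCS effect. With 16 per arm:

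- session main effect (the natural test of Hypothesis 2): average change = [μ + (μ + δ)]/2 = μ + δ/2. It is non-zero whenever μ is non-zero, even if δ = 0.
- stimulation-by-session interaction: (μ + δ) − μ = δ. This is the tDCS question.
- group main effect on raw scores with baseline as one of the two time levels: after randomisation the expected baseline difference is 0, so the expected contrast is (0 + δ)/2 = δ/2. It dilutes the effect and carries chance baseline imbalance.
- group effect on change-from-baseline scores: δ again, the same contrast as the interaction when there are two time points.

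**Inputs.** From the documents: N = 32, 16 per arm; a two-sided alternative; four primary outcomes. N = 32 comes without alpha, power, effect size or SD, so it cannot be reproduced and is taken as given. Assumed, because the documents are silent: alpha 0.05; a common change d in baseline-SD units with equal SDs; pre-post correlation r of 0.3 to 0.7; δ = 0.

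**Formula.** Standardised change dz = d/√[2(1 − r)]. The paired t test on 32 participants has 31 df and noncentrality dz√32. For d = 0.5 and r = 0.5, dz = 0.5/√1 = 0.5, the noncentrality is 0.5 × 5.657 = 2.83, the critical value is 2.04 and the rejection probability is 0.782.

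| Change d | r = 0.3 | r = 0.5 | r = 0.7 |
|---|---|---|---|
| 0.2 SD | 15% | 20% | 29% |
| 0.3 SD | 28% | 38% | 56% |
| 0.5 SD | 64% | 78% | 94% |
| 0.8 SD | 96% | 99% | >99.9% |

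Using the mixed-ANOVA error df of 30 changes no entry by more than about 0.1 percentage point. Rejection passes 50% at dz = 0.36 and 80% at dz = 0.51.

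**Sensitivity.**

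- Alpha 0.0125 (0.05 split over four outcomes): 19%, 57.5% and 96% at dz 0.3, 0.5 and 0.8; 50% is reached at dz 0.46.
- 24 completers (assumed), alpha 0.05: 65% at dz 0.5 and 96% at dz 0.8.
- Within one arm of 16 instead of pooled: 20% at dz 0.3, 46.5% at dz 0.5 and 85% at dz 0.8.
- At least one of four outcomes, unadjusted, outcome correlation 0.5 to 0 (simulation, 20,000 runs): 70–85% at dz 0.3 and 96–99.8% at dz 0.5.

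**Comparison.** In the same simulation the interaction was rejected in 4.8–5.2% of runs per outcome, whatever the common change.

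**The case against.** The between-arm question is already primary. Hypothesis 1, the main objective, the superiority framework and the pre-specified interaction all address it. No sentence says that rejecting Hypothesis 2 would support tDCS. A session main effect is routine output of a mixed ANOVA, and documenting change over treatment is legitimate. All of that stands. A reader might infer that the trial lacks a valid test of tDCS, and the documents do not support that.

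Nor do the percentages above show an inflated false-positive rate. If patients improve on CBT, the null of no change is false and rejecting it is correct. The error rate of Hypothesis 1 is untouched.

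A reader might also infer that Hypothesis 2 will probably be rejected. The documents give no CBT change, SD or correlation, so that cannot be asserted. At 0.2 SD rejection is unlikely, and at 0.3 SD it exceeds one half only towards the upper end of the assumed correlations. Pooling is itself an inference: the session main effect makes it the likelier reading, but a within-arm reading is open and has less power.

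Practice should not be pressed. Three of the four primary outcomes are rating scales, and the tasks repeated weekly are secondary outcomes.

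Finally, it would be too strong to say that a group main effect can never bear on tDCS. Section 1 defines the primary endpoints as changes from baseline. If change scores are what is analysed, the group effect is the between-arm difference in change.

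What survives is the formal status. Hypothesis 2 is written with its own null and alternative, parallel to Hypothesis 1. If it was meant only descriptively, the plan should say so.

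**Conclusion.** The point holds in a limited form and is worth correcting. It follows from the text alone that a primary null ignores the randomised comparison, that everyone receives CBT, and that the SAP leaves open which of three ANOVA terms is decisive. Rejecting Hypothesis 2 is not evidence for tDCS.

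The size is conditional. Under the pooled reading with N = 32, no tDCS effect and two-sided 5%, rejection on a single outcome is more likely than not only if the mean change exceeds about 0.36 SD of change. How close the trial comes to that depends on a CBT response that the documents do not quantify. The fault is one of hypothesis status and interpretation. It does not invalidate the interaction test.

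**What to change.** 1. Take Hypothesis 2 out of the primary hypotheses. Report change over time by arm, with confidence intervals, as descriptive or supportive.
2. State that the confirmatory test is the between-arm difference in change, and choose one form in advance: the stimulation-by-time interaction on raw scores (equivalently, with two time points, the group effect on change-from-baseline scores), or the baseline-adjusted arm difference at week 8.
3. State in the SAP whether raw or change scores enter the ANOVA. Add that neither a session main effect nor a group main effect on raw scores that include baseline will be taken as evidence for tDCS.
4. Treat the secondary Hypothesis 2 in the same way.

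This changes protocol and SAP wording only; visits, data collection and sample size are unaffected. The downside is one fewer claim that could be called positive.
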